## Add Related Grants

If applicable, please search for and select the OSPA Account number or Electronic Internal Approval Form (eIAF) # (notif #) associated with this IRB application using the "Add Related Grants" button.  
If required by your funding agency, upload your grant using the "Grant/Contract Attachments" button.

[Add Related Grants](#)

[Grant/Contract Attachments](#)

The research involves use of Department of Defense (DoD) funding, military personnel, DoD facilities, or other DoD resources. (See [DoD SOP](#) and [DoD Summary](#) for details)

Yes  No

Using the "attachments" button (below), attach applicable materials addressing the specific processes described in the DoD SOP.

[DOD SOP Attachments](#)

Additional Certification: (If your project is federally funded, your funding agency may request an Assurance/ Certification/Declaration of Exemption form.) Check the following if needed:

Protection of Human Subjects Assurance/Certification/Declaration of Exemption (Formerly Optional Form – 310)

Assurance/Certification Attachments

## OTHER REVIEW COMMITTEES

0 unresolved  
comment(s)

If you check any of the below committees, additional materials may be required with your application submission.

Does your research fall under the purview of any of the other review committees listed below? [If yes, check all that apply and attach applicable materials using the attachment button at the bottom of your screen.]

Yes  No

**Additional Information**

Institutional Biosafety Committee

Radiation Safety Committee

Radioactive Drug Research Committee

Markey Cancer Center (MCC) Protocol Review and Monitoring Committee (PRMC)

Graduate Medical Education Committee (GME)

Office of Medical Education (OME)

- [Institutional Biosafety Committee \(IBC\)](#) - Attach required IBC materials
- [Radiation Safety Committee \(RSC\)](#) - For applicability, see instructions and attach form
- [Radioactive Drug Research Committee \(RDRC\)](#)
- [Markey Cancer Center \(MCC\) Protocol Review and Monitoring Committee \(PRMC\)\\*\\*](#) - Attach MCC PRMC materials, if any, per instructions.
- [Office of Medical Education \(OME\)](#)
- [Graduate Medical Education Committee \(GME\)](#)

Attachments

**\*\* If your study involves cancer research, be sure to select "Cancer Research" in the "Research Attributes" section.** ORI will send your research protocol to the Markey Cancer Center (MCC) Protocol Review and Monitoring Committee (PRMC). The [MCC PRMC](#) is responsible for determining whether the study meets the National Cancer Institute (NCI) definition of a clinical trial and for issuing documentation to you (the investigator) which confirms either that PRMC approval has been obtained or that PRMC review is not required. Your IRB application will be processed and reviewed independently from the PRMC review.

**ADDITIONAL INFORMATION/MATERIALS****0 unresolved  
comment(s)**

Do you want specific information inserted into your approval letter?  Yes  No

**Approval Letter Details:**

If you wish to have specific language included in your approval letter (e.g., serial #, internal tracking identifier, etc...), type that language in the box below exactly as it should appear in the letter. The text you enter will automatically appear at the top of all approval letters, identical to how you typed it, until you update it. Don't include instructions or questions to ORI staff as those will appear in your approval letter. **If these details need to be changed for any reason, you are responsible for updating the content of this field.**

**Additional Materials:**

If you have other materials you would like to include for the IRB's consideration, check all that apply and attach the corresponding documents using the Attachments button below.

Detailed protocol  
 Dept. of Health & Human Services (DHHS) approved protocol (such as NIH sponsored Cooperative Group Clinical Trial)  
 Other Documents

**Protocol/Other Attachments**

Attach	Type	File Name
Other		PHI for NIH Data Archive.docx

NOTE: [Instructions for Dept. of Health & Human Services \(DHHS\)-approved protocol](#)

If you have password protected documents, that feature should be disabled prior to uploading to ensure access for IRB review.

To view the materials currently attached to your application, click "All Attachments" on the left menu bar.

**SUBMISSION INFORMATION****0 unresolved  
comment(s)**

**\*\*\* If this Continuation Review entails a change in the scope of your activities to include COVID-19 related research, please insert "COVID19" at the start of your Project and Short Titles.\*\*\***

Each Section/Subsection in the menu on the left must have a checkmark beside it (except this Submission section) indicating the Section/Subsection has been completed. Otherwise your submission for IRB review and approval cannot be sent to the Office of Research Integrity/IRB.

If applicable, remember to update the Approval Letter Details text box under the Additional Information section

If your materials require review at a convened IRB meeting which you will be asked to attend, it will be scheduled on the next available agenda and you will receive a message to notify you of the date.

If you are making a change to an attachment, you need to delete the attachment, upload a highlighted version that contains the changes (use Document Type of "Highlighted Changes"), and a version that contains the changes without any highlights (use the appropriate Document Type for the item(s)). Do **not** delete approved attachments that are still in use.

## Statistical Design and Power

### Statistical Design

**Study Feasibility.** Clinician and patient enrollment, a measure of feasibility of a large RCT, will be assessed by reporting percentages for the 6 clinician and 5 patient enrollment variables. Rates of treatment and assessment completion will also be reported. Clinician adherence will be evaluated by coding 20% of treatment sessions according to a UP adherence checklist and reporting adherence rates within each condition.

**Study and Treatment Acceptability.** Quantitative measures of study and treatment acceptability (e.g., the AFQ, Clinician and Patient Versions) will be assessed through the use of descriptive statistics. Qualitative analyses of clinician and patient perceptions of study and treatment protocols will be analyzed in conjunction with quantitative results (e.g., QUAL + QUAN). Qualitative analysts will review interview recordings and transcriptions, identifying and coding the primary issues raised by respondents using a grounded theory, embedded in Willms, et al.'s guidelines for coding: reaching consensus on coding assignment, identifying concordance among codes, and using the process of constant comparisons to generate a taxonomy of themes and identify their relationships to one another. This will have analysts: 1) review all transcripts to develop a broad understanding of the content and document initial impressions of topics and themes, defining the boundaries of specific codes, 2) independently code empirical material to condense data into analyzable units and form a codebook, 3) discuss disagreements in code assignment/description (each test will be reviewed by at least two analysts), 4) compare reliability of assigning the same codes to identical text segments, and 5) use the computer program *NVivo* to examine the association between different a priori and emergent categories.

**Pilot Test of Personalization Aims (ordering and discontinuation).** In addition to our primary aim of establishing the feasibility/acceptability of our personalization strategies and study design, we seek to determine whether a preliminary signal exists to support the notion that personalized sequencing and target-informed discontinuation can enhance treatment efficiency. First, to explore whether personalized sequencing leads to more efficient improvements in the core process addressed by the UP, we will use hierarchical linear mixed modeling (HLMM) to compare the average rate of change in clinical outcomes among the three UP sequencing conditions (UPS, UPP-CA, and UPP-CO). The primary outcome measure for aim is the distress aversion subscale from the MEAQ (MEAQ-DA), which has previously been used to demonstrate target engagement with the UP (see Preliminary Studies). Additionally, to examine whether core process engagement can serve as an early indicator of treatment response, prompting discontinuation, we will assess variability in MEAQ-DA levels at the second stage randomization (S5 assessment), along with the degree to which any patients randomized to discontinue demonstrate additional symptom improvement (using HAM-A ratings) in the absence of treatment such that they are responders by the W20 assessment. We will also explore whether patterns exist between S5 MEAQ-DA scores and responder status for those that discontinued after session 6.

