We will use a treatment window during which the assigned number of sessions will be completed; specifically, patients randomized to the Brief condition will complete 7 sessions during an 10-week window and patients randomized to the Full condition will complete 13 sessions during a 20-week window. This will allow us to account for scheduling challenges (e.g., patient/therapist illness, vacation). The first session for all participants will be an "orientation to treatment" session in which presenting concerns will be reviewed and an overview of the treatment model will be provided. As noted previously, the skills delivered during the remaining sessions in this study will be drawn from the UP. Four of the five UP modules will be implemented 2 sessions: Understanding Emotions, Mindful Emotion Awareness, Cognitive Flexibility, and Increasing Interoceptive Tolerance. The 5th UP module, Countering Emotional Behaviors, is designed to be implemented in 4 sessions. All sessions will last for 60 minutes in duration. Thus, depending on treatment length and module order, each participant will receive 2 to 5 UP modules during this study. It is important to note that the therapeutic strategies involved in all modules are all common, evidence-based cognitive-behavioral strategies and are not, themselves, under study; instead, we are interested in whether personalized sequencing leads to faster improvements (not whether patients improve at all - we expect that most will improve). Every module involves reading from a published manual (the Unified Protocol for the Transdiagnostic Treatment of Emotional Disorders; Barlow et al., 2018) and completing homework assignments outside of the treatment session (this intervention has previously been reviewed by UK's non-medical IRB). These treatment sessions will be audio-recorded provided participants give their consent for this; this will allow study staff to rate sessions for fidelity to the protocol.

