Clinician Participants will be asked to attend a one-day training workshop on the Unified Protocol. The PI, [name], was the founding director of the Unified Protocol Institute in her previous academic position at Boston University; in this role, she routinely provided this training, which will consist of didactic lecture and role plays. After the workshop, clinicians will be asked to begin implementing the UP with patients on their caseload that have consented to participate in this study. Clinicians will also attend weekly consultation calls with the PI who will provide additional guidance on the delivery of the study intervention; clinicians will be asked to participate in these calls for the duration of time they have study patients on their caseload. Clinicians will be asked to audio-record their work delivering the UP with their study patients; these tapes will be rated for adherence and competence with the protocol (see attached adherence checklists that study staff will use to rate tapes). Study staff will provide clinicians these audio-recorders for the duration of the study; study staff will stop by clinicians' offices to pull recordings off the audio recorder and upload them directly to the UK provided, password-protected TIPS lab server space. Finally, clinicians will be asked to fill out questionnaires at several time points during the study: 1) directly following provision of their informed consent, 2) following completion of the didactic workshop, and 3) after all patient treatment has been completed. Following their provision of informed consent, all questionnaires will be collected via an email with a link to an online REDCap survey.

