### Benefits

- Describe potential direct benefits to study participants – including diagnostic or therapeutic, physical, psychological or emotional, learning benefits. This cannot include incentives or payments.
- State if there are no direct benefits.
- Describe potential benefits to society and/or general knowledge to be gained.

Describe why potential benefits are reasonable in relation to potential risks. If applicable, justify why risks to vulnerable subjects are reasonable to potential benefits.

The primary risk in the current study is termination of treatment before symptom remission is achieved for those in the Brief condition. Participants will be informed about this risk on the phone screen and at Assessment Visit 1. It is important to note, however, that the average number of sessions community patients typically attend is 5, which suggests that this risk may be no greater than what is experienced in usual care. Additionally, a large proportion of symptom improvement occurs within the first 5 sessions of treatment (Fennell & Teasdale, 1987; Lutz, Stulz, & Köck, 2009), further mitigating this risk. Finally, in the event that participants in the Brief treatment are at an imminent risk of harm to themselves or others at their final session, they will be brought to the attention of the PI to

develop a safety plan with the participant which may include referrals to other psychotherapy resources or hospitalization.

Participants may experience some interference with daily activities due to scheduling of sessions. Additionally, some patients may find answering the questionnaires uncomfortable because of the sensitive nature of some of the questions (e.g., asking about symptoms of anxiety). In any of the modules the primary risk is the evocation of uncomfortable levels of anxiety or other emotions during the sessions. Some patients may find sessions stressful and react to them with anxiety. However, it is not expected that anxiety will be higher than would be experienced in real life situations or in the course of usual and customary clinical treatment. Participants will be informed about these risks and told that they may withdraw from the study at any time and may refuse to complete any procedures they find too uncomfortable.

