### Data and Safety Monitoring

The IRB requires review and approval of data and safety monitoring plans for greater than minimal risk research or NIH-funded/FDA-regulated clinical investigations.

- If you are conducting greater than minimal risk research, or your clinical investigation is NIH-funded, describe your Data and Safety Monitoring Plan (DSMP). [Click here for additional guidance on developing a Data and Safety Monitoring Plan](#).
- If this is a non-sponsored investigator-initiated protocol considered greater than minimal risk research, and if you are planning on using a Data and Safety Monitoring Board (DSMB) as part of your DSMP, [click here for additional guidance](#) for information to include with your IRB application.

Data will be collected and entered continuously throughout the project. There are no plans for independent data and safety monitoring. The PI will be responsible for managing unanticipated problems, adverse events, and data quality. All cases seen in this study will be supervised by the PI, which will allow for continuous monitoring of adverse events or clinical worsening.

No PHI will be shared with NIH. NIH's Data Archive system will read, but not store, the following PHI: patients' first name, middle name, last name, their birthdate, and birth city. NIH will assign a unique code to this combination of values for each patient but will not store patients' data to ensure the data is de-identified. After the completion of the study, study staff will remove this information from locally-stored files.

[Back to Top](#)

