### Power Analyses.

This proposal is designed as a pilot trial to, as noted in the RFA, collect relevant data to inform the design (and increase the likelihood of obtaining meaningful results) in a subsequent well-powered trial. To do this, we are measuring potential mechanisms of change and exploring preliminary effect sizes and the variability of treatment effects. This will allow us (and future reviewers) to determine whether further testing is warranted.

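### The risk named as primary, stopping before remission in the Brief arm, has no by-arm count: the discontinuation analysis asks only about further improvement among patients who stopped

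*Combined protocol and SAP*

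**What the plan says.** **The risk.** Under Potential Risks & Benefits: "The primary risk in the current study is termination of treatment before symptom remission is achieved for those in the Brief condition".

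**The analysis.** The paragraph on the pilot test of the personalization aims (Statistical Design) plans two looks at discontinuation. One is "the degree to which any patients randomized to discontinue demonstrate additional symptom improvement (using HAM-A ratings) in the absence of treatment", carried to responder status at the W20 assessment. The other is "whether patterns exist between S5 MEAQ-DA scores and responder status for those that discontinued after session 6". Both are confined to patients who stopped. The mixed model in the same paragraph compares the three module-ordering conditions, not the two lengths.

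**The purpose.** Power Analyses says of the pilot's data: "This will allow us (and future reviewers) to determine whether further testing is warranted".

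**The monitoring.** Data and Safety Monitoring plans no independent monitoring and states: "All cases seen in this study will be supervised by the PI, which will allow for continuous monitoring of adverse events or clinical worsening". The risk-minimisation list under Records, Privacy, and Confidentiality adds weekly meetings of the PI with research staff and clinicians. It also says that a patient judged clinically to be deteriorating significantly, or to be developing active suicidal potential, is taken out of the study and referred.

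**The data.** Research Procedures has every participant complete a weekly battery for 20 weeks, which Brief patients continue after treatment ends, and attend Assessment Visits 2 to 4. The measure schedule puts OASIS, ODSIS and C-SSRS items 1-6 in the weekly battery, and HAM-A, HAM-D and the full C-SSRS at assessment visits.

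**The concern.** A pilot meant to decide whether early stopping deserves a larger trial should report the harm it names first next to the benefit it hopes for. Here the benefit side has a planned analysis and the harm side has none. Responder status does identify non-responders, but it puts the patient who stayed the same with the one who got worse. It is also not remission, and the Statistical Design section defines neither term. With no Full-arm figure alongside, even a sound count in the Brief arm could not be read as an effect of stopping.

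Removal for deterioration makes this worse. The documents do not say whether a removed patient is still assessed at W20. If not, the clearest failures become missing data, and the responder proportion among those left is too favourable. The signal carried into the next trial's design could then be one-sided.

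**Working it through.** The documents give no figure to reproduce: there is no power calculation, no deterioration rate and no allocation ratio for length.

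**1. What is collected against what is analysed**

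| Information | Collected in both arms? | Planned analysis by length arm? |
|---|---|---|
| Remission | Not defined | None |
| HAM-A | Assessment visits | None; stopped patients only, improvement to responder status |
| HAM-D, full C-SSRS | Assessment visits | None |
| OASIS, ODSIS, C-SSRS items 1-6 | Weekly, 20 weeks | None |
| Visit 4 (46 to 50 weeks after Assessment 1) | Yes | None |
| Removal or referral for deterioration | Happens under the safety rule | None |

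The middle column is nearly full and the right-hand column is empty.

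**2. Equality of schedule.** The weekly battery runs 20 weeks in each arm, a ratio of 20/20 = 1.00. The Brief session window closes at week 10 ("patients randomized to the Brief condition will complete 7 sessions during an 10-week window"), which leaves 20 - 10 = 10 weekly batteries after it. Clinician contact is not equal, since "patients randomized to the Full condition will complete 13 sessions during a 20-week window". The ratio is 10/20 = 0.50 in weeks and 7/13 = 0.54 in sessions. Research Procedures also gives 6 and 12 sessions (6/12 = 0.50) and ties the end of the Full window to weeks 13-16 (10/16 = 0.63 to 10/13 = 0.77). This imbalance matters only for items that rely on clinician contact, such as removals.

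**3. Effect of removals on the responder proportion.** Suppose a fraction *d* of the arm is removed and none of these would have responded. The proportion among those remaining is then 1/(1 - *d*) times the proportion among all randomised. The documents give no *d*. For assumed values of 5%, 10% and 20%:
- 1/0.95 = 1.05
- 1/0.90 = 1.11
- 1/0.80 = 1.25

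**4. What a by-arm count could show.** Assume 1:1 allocation. The totals are 50 (enrolled to date, all treated as patients), 60 and 80 (two statements of planned completers) and 150 (Study Design). The bound for zero events is 1 - 0.05^(1/n), and the intervals are exact (Clopper-Pearson). Power is two-sided at 0.05 for an assumed 20% against 10% worsening.

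| Total | Per arm | One-sided 95% upper bound, 0 events | Exact 95% CI near 10% | Power, 20% v 10% |
|---|---|---|---|---|
| 50 | 25 | 11.3% | 2/25: 1.0 to 26.0% | 16% |
| 60 | 30 | 9.5% | 3/30: 2.1 to 26.5% | 19% |
| 80 | 40 | 7.2% | 4/40: 2.8 to 23.7% | 24% |
| 150 | 75 | 3.9% | 8/75: 4.7 to 19.9% | 40% |

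Length is randomised only before Session 5, so earlier dropouts never enter a length arm. The enrolment-based arm sizes are therefore upper limits.

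**5. Timing.** Statistical Design relies on a W20 assessment. Research Procedures places Visit 3 at weeks 13-16 and calls that the end of the Full window, which it elsewhere puts at 20 weeks. HAM-A is not in the weekly battery, so no scheduled visit clearly yields a week-20 HAM-A. Visit 4 is described as repeating the questionnaires, while the measure schedule lists HAM-A and HAM-D for assessment visits generally.

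**The case against.** The best reply is that this is a feasibility and acceptability pilot with no power calculation, that the risk is disclosed and managed, and that the planned analysis is not blind to failure. Non-responders are the complement of responders. Objective 2 concerns post-treatment symptom change, which can go either way, and Power Analyses mentions the variability of treatment effects. All of this is fair, and it limits the point to a descriptive table. It does not supply a comparison by length arm or a count of patients who got worse.

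Three stronger readings are tempting, and the documents do not support them.

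- *Worsening is seen only through sessions, so Brief patients go unobserved after week 10.* The weekly battery with C-SSRS items continues to week 20 in Brief, Visits 3 and 4 apply to everyone, and research staff attend the weekly safety meetings. The consultation calls follow the clinician's caseload, not each patient's exit: "clinicians will be asked to participate in these calls for the duration of time they have study patients on their caseload". Any figure that assumes no detection in Brief after week 10 therefore has no footing.
- *Adverse-event comparisons are biased in favour of Brief.* No such comparison is planned. Shorter clinician contact is a caution for reading removals, no more.
- *The trial cannot show the harm.* It collects the data that could. What is missing is a plan to analyse them by arm.

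**Conclusion.** The point holds as a gap in the analysis plan. The risk called primary is never tabulated, the discontinuation analysis has no Full comparator and does not separate unchanged from worse, and removal for deterioration could take the worst outcomes out of the W20 responder count. That these data are collected but not analysed by arm rests on the documents' text alone.

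The sizes rest on assumptions. Removal of 5% to 20% would inflate the responder proportion by a factor of 1.05 to 1.25, if removed patients are unassessed and none would have responded. A table at 25 to 75 per arm (1:1 assumed) would exclude, with zero events, true rates above 11.3% down to 3.9%. It would have 16% to 40% power for 20% against 10%. That is enough to describe and not enough to test. The change is worth making because it is cheap and keeps a single-arm improvement result from standing alone. It does not call the trial's conduct or data collection into question.

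**What to change.** Add to the pilot-test paragraph of Statistical Design a descriptive table by randomised length arm. Keep all patients randomised to length in the denominator. Give the number, proportion and exact 95% confidence interval of patients:

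- (a) not in remission at the W20 assessment, with remission and response both defined;
- (b) with a HAM-A or HAM-D score above the S5 value by a prespecified margin, at W20 and at Visit 4 where these are collected;
- (c) with worsening on weekly OASIS or ODSIS by a prespecified margin;
- (d) with new C-SSRS ideation or behaviour;
- (e) removed or referred for deterioration.

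Count group (e) as non-responders. Note that (e) depends partly on clinician contact, which is shorter in Brief. Report missing scores by arm, and place the table beside the W20 responder result.

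Before this can be programmed, the documents must reconcile the W20 assessment with Visit 3 at weeks 13-16, the end of the Full window, the content of Visit 4, the session counts (6 and 12 against 7 and 13) and the sample sizes (60, 80 and 150).

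The cost is one paragraph and one table, using data already scheduled for collection. The downside is small counts and wide intervals, so the table should carry no test and no claim of safety.
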